1. BACKGROUND AND RATIONALE

Gastric cancer is the second most common cause of cancer death worldwide. Surgery is the mainstay treatment for cure. Peritoneum is a common site of recurrence and the prognosis in patients with peritoneal recurrence is dismal. Hence, prevention is essential to patient's outcomes. In patients with serosal invasion, about half experience peritoneal recurrence within first 2 years after surgery, even after curative surgery. Peritoneal metastasis is caused by the implantation of free cancer cells in the peritoneal cavity exfoliated from the primary tumor before or during curative surgery. It is well known that cancer cells spillage could occur during surgery due to manipulation or even after lymph node dissection. If we can remove these free exfoliated cancer cells on the peritoneal lining, we may reduce the risk of tumor recurrence.

Recently, a study has demonstrated a dramatic reduction of peritoneal recurrence with extensive peritoneal lavage in patients who underwent curative resection of gastric cancer. Extensive peritoneal lavage was performed after the curative operation. The peritoneal cavity was washed with normal saline which is then followed by the complete aspiration of the fluid. This procedure was done 10 times using 1 liter of normal saline. The method was based on the 'limiting dilution theory' in which the method can dilute the number of free cancer cells to minimal hence reduce the risk of tumor implantation. In this study, among patients with microscopic peritoneal metastasis, peritoneal recurrence developed in 40% of patients with extensive peritoneal lavage and surgery, compared to 89.7% in patients with surgery alone. Extensive peritoneal lavage carries minimal risk to patients. It is simple and inexpensive, and it is not time consuming. Hence, it may be an effective strategy for treatment of gastric cancer.

1.1. General Introduction

Gastric cancer is the second most common cause of cancer death worldwide. Surgery is the mainstay treatment for cure. Peritoneum is a common site of recurrence and the prognosis with peritoneal recurrence is dismal. Hence, any measure that can prevent peritoneal relapse will significantly improve treatment outcomes. There is recent evidence suggesting that extensive peritoneal lavage with large volume of normal saline after surgery before abdominal closure can reduce risk of peritoneal recurrence and enhance overall survival.

1.2. Rationale and justification for the Study

Significance: Because of the simplicity of this technique, the outcome of this study can change clinical practice in surgery for gastric cancer in the future

Hypothesis: Extensive peritoneal lavage improves the overall survival of patients with gastric cancer who undergo gastrectomy by reducing the risk of peritoneal recurrence.

a. Rationale for the Study Purpose

Peritoneum is a common site of recurrence and the prognosis with peritoneal recurrence is dismal. We performed a study of the outcomes of our patients who received radical gastrectomy for cancer in our prospective gastric cancer database. Out of 273 patients, recurrence was developed in 83 patients (30%) in which 20% were at the peritoneum. Among patients with serosal invasion, 30% of patients developed peritoneal recurrence during follow-up. Hence, peritoneal recurrence is a major clinical problem.

b. Rationale for Study Population

The study population are patients with T3 or T4 gastric cancer based on clinical staging. These groups of patients have highest risk of peritoneal recurrence

c. Rationale for Study Design

This is a randomized controlled study to evaluate the benefits of extensive peritoneal lavage as a prophylactic strategy for preventing peritoneal recurrence in patients with gastric cancer.

2. HYPOTHESIS AND OBJECTIVES

To compare the outcomes between extensive peritoneal lavage and standard treatment for patients with curative gastrectomy for gastric cancer.

2.1. Hypothesis

Extensive peritoneal lavage significantly improve the overall survival of patients by reducing the risk of peritoneal recurrence.

2.2. Primary Objectives

Overall survival

2.3. Secondary Objectives

Disease free survival

Peritoneal recurrence rate

2.4. Potential Risks and benefits:

a. End Points - Efficacy

The primary endpoint of the study is overall survival. Secondary endpoints are disease-free survival and the frequency of peritoneal recurrence.

b. End Points - Safety

Safety Data will be monitored. Complications of peritoneal lavage are rare and includes

- Injury to the viscera during lavage
- Intra abdominal bleeding.

3. STUDY POPULATION

3.1. List the number of subjects to be enrolled.

The total target number of enrollment is 800 research subjects by 23 centres in the region (refer to table 1 below for recruitment projection) There are no restrictions based on gender and race. There may be a doctor-patient relationship but the rejection to participate in the study of not allowing the research team to perform the peritoneal lavage will not compromise with the treatment rendered to the patient. The patient will still receive the standard of care should they not allow the excess peritoneal lavage for the research. The study will involve inpatients and outpatients subjects.

Table.1 All participating sites for EXPEL trial

Country	Site	Recruitment Target
China	Nanfeng Hospital, Southern Medical University	78
	Peking University Cancer Hospital	150
Hong Kong	PWH, Chinese University of Hong Kong	5
	QMH, University of Hong Kong	35
Japan	Aichi Cancer Centre Hospital, Japan	12
	Fukushima Medical University, Japan	8
	Gifu University Hospital, Japan	12
	Kanagawa Cancer Centre, Japan	12
	National Cancer Centre East Hospital, Japan	12
	Niigata Cancer Center Hospital, Japan	12
	Shizuoka Cancer Centre, Japan	65
	Korea	Ajou University, Korea
Gyeongsang National University Jinju Hospital, Korea		10
National Cancer Centre, Korea		10
Seoul National University Bundang Hospital, Korea		60
Seoul National University Hospital, Korea		130
Seoul St Mary's Hospital-The Catholic University of Korea		23
The Catholic University of Korea Uijeongbu St. Mary Hospital, Korea		5
Yonsei University College of Medicine, Korea		23
Malaysia	National University of Malaysia	14
	University Malaya Medical Centre (UMMC) Kuala Lumpur, Malaysia	10
Singapore	Tan Tock Seng Hospital, Singapore	8
	National University Hospital, Singapore	32
Sub-total	All Centres	800

3.2. Criteria for Recruitment

Potential subjects will be identified by study team. Clinicians from the study team will make the first contact with subjects. The clinician will assess patient suitability for study and inform patient about this clinical trial. The research nurse will recruit the potential subjects by a face-to-face contact when they come for their prospective regular clinic visits.

3.3. Inclusion Criteria

1. Patients who have T3 (subserosal) or T4 (serosal) disease based on CT TAP scan and intra-operative inspection with any N staging and M0 gastric cancer.
2. Patients planned for open or laparoscopic gastrectomy.
3. Patients undergoing gastrectomy with curative intent.
4. Lower age limit of research subjects 21 years old and upper age limit of 80 years old.
5. Ability to provide informed consent
6. Ability to come back for study visits throughout the 5 years duration after surgery
7. Patients are local residents

3.4. Exclusion Criteria

1. Patients who undergo a palliative gastrectomy.
2. Patients who undergo a gastrectomy as emergency.
3. Vulnerable persons under age of 21.
4. Patients receiving neoadjuvant therapy.
5. Patients presented with life-threatening bleeding from tumour
6. ASA score of 4 & 5
7. Patients with another primary cancer within last 5 years
8. Patients with gross peritoneal and liver metastasis at surgery.

3.5. Withdrawal Criteria

Study closure due to DSMB review.

3.6. Subject Replacement

Subjects who drop out will not be replaced.

4. TRIAL SCHEDULE

The length of time of the subject's direct involvement in the study coincides with clinical visits. The subject will be followed up post operatively during routine outpatient clinical visits for 5 years to assess survival and spread of cancer or recurrence after surgery.

1. There will be 4 visits each in the first year & second year (Every 3 monthly)
2. Follow by half-yearly by the 3rd year
3. Yearly at the 4th and 5th year

[figure not shown]
5. STUDY DESIGN

It is a multi-center randomized controlled study. Patients with locally advanced gastric cancer (clinically T3 or T4, M0 disease) who are undergoing radical gastrectomy with curative intent will be recruited. After gastrectomy and before abdominal wall closure is performed, patients who had consented will be randomized into 2 arms: a study arm in which the peritoneal cavity will be washed with 10 liters of normal saline (1 liter each cycle for 10 cycles); and a control arm in which ≤ 2 liters of lavage will be performed. The surgery time for patients in the study arm will be approximately 20 minutes longer than patients in the control arm. Patients will be followed up as per routine practice. The primary endpoint is overall survival. Secondary endpoints are disease-free survival and frequency of peritoneal recurrence.

5.1. Summary of Study Design

Briefly describe the study design and indicate, in general terms, how the design will fulfil the intent of the study.

EXPEL – GC

6. METHODS AND ASSESSMENTS

It is a multi-centre randomized controlled study. Patients with locally advanced gastric cancer (clinically stage T3 or T4 and M0 based on AJCC 7th edition) who underwent radical gastrectomy with curative intent will be recruited. Before abdominal wall closure after the curative gastrectomy is performed, patients will be randomized into 2 arms: a study arm in which the peritoneal cavity will be washed with 10 litres of normal saline; and a control arm in which standard surgery with ≤ 2 litres of lavage will be performed. Patients will be followed up at as per routine practice. The primary endpoint is overall survival. Secondary endpoints are disease-free survival and frequency of peritoneal recurrence.

Randomisation and Blinding

Study participants will be randomized to study arm and control arm using computer generated code. The patients will be stratified according to individual study site. Potential subjects are identified based on prospective imaging. Primary registration and study consent will be obtained from the potential subjects. Patients with clinical T3 or T4 gastric cancer on inspection at surgery will be formally recruited into the study. The randomisation code will be disclosed to the surgeon only at the end of gastrectomy. Extensive or standard lavage will then be performed according to the randomisation code. The abdomen will then be closed as per standard.

6.1. Contraception and Pregnancy Testing

Not Applicable

Schedule of Events

	Visit window*	Informed Consent	Medical History	Physical Examination	CT TAP Scan	Inclusion/Exclusion	Randomisation	Peritoneal Lavage	Adjuvant Therapy	AE/SAE reporting**	Documentation
Screening Baseline	+/- 14 days	X	X	X	X	X				X	Fill registration form (section A) & on-study form (section B)
Surgery	+/- 7 days			X		X	X	X		X	Complete registration form (section A) & OT form (section C).
Post-op visit week 2	+/- 7 days			X						X	Surgery treatment form (section D)
Study visit 1	+/- 30 days			X					X	X	Complete follow-up form (section E)
Study visit 2	+/- 30 days			X					X	X	Complete follow-up form (section E)
Study visit 3	+/- 30 days			X					X	X	Complete follow-up form (section E)
Study visit 4/ 1 st year follow up	+/- 60 days			X	X				X	X	Complete follow-up form (section E)
Study visit 5	+/- 30 days			X					X	X	Complete follow-up form (section E)
Study visit 6	+/- 30 days			X					X	X	Complete follow-up form (section E)
Study visit 7	+/- 30 days			X					X	X	Complete follow-up form (section E)
Study visit 8/ 2 nd year follow up	+/- 60 days			X	X				X	X	Complete follow-up form (section E)
Study visit 9	+/- 30 days			X					X	X	Complete follow-up form (section E)
Study visit 10/ 3 rd year follow up	+/- 60 days			X	X				X	X	Complete follow-up form (section E)
Study Visit 11 / 4 th year follow up	+/- 180 days			X	X				X	X	Complete follow-up form (section E)
Study Visit 12 / 5 th year follow up	+/- 180 days			X	X				X	X	Complete follow-up form (section E)

*Filing of protocol deviation form (section G) is mandatory if any of the above visit fails to occur within the visit window; however, should the visit day fall short within acceptable range of 1-2 weeks outside the visit window due to scheduling difficulties, no protocol deviation filing is required.

** Reporting of AE/SAE events should be done through the AE/SAE form (section H)

7. SURGICAL TREATMENT

Potential candidates will be given the same treatment option as other gastric cancer patients. At the start of surgery, 100ml of normal saline will be infused into patient's peritoneal cavity. The saline containing cells will then be collected by suction for cytological examination. A standard D2 lymph node dissection based on Japanese gastric cancer classification will be performed on candidates. Techniques for lymph node dissection may involve diathermy, energy sealing, mechanical clips or suture ligation. After reconstruction, prior to wound closure, suitable patients will then be randomized to undergo either a standard peritoneal lavage (<2l) or extensive peritoneal lavage (10l). Following peritoneal washing the rest of the operation would proceed as per routine.

Patients with intraoperative staging of T3/T4, any N, M0 stage will be included in to the study even if histopathology turned out to be T1/T2 or M1. They will be put under intention to treat group. It will be considered as screen failure if patient is found to be non-T3/T4 stage or have metastasis during operation.

Patients undergoing completion gastrectomy will be included in to the study if the partial gastrectomy is for benign ulcer or was done more than 5 years ago.

8. SAFETY MEASUREMENTS

8.1. Definitions

Serious Adverse Event

What is a Serious Adverse Event?

An adverse event is considered **serious** if it results in any of the following outcomes:

- Death due to any cause
- A persistent or significant incapacity or substantial disruption of the ability to conduct normal life functions
- Hospitalization (inpatient admission or overnight stay) or prolongation of hospitalization.
- An immediately life-threatening adverse event (the occurrence places the subject at immediate risk of death. It does not include an adverse event that, had it occurred in a more severe form, might have caused death.

Important medical events that may not result in death, be life-threatening, or require hospitalization readmission within 30 days post procedure may be considered serious when, based upon appropriate medical judgment, they may jeopardize the patient or subject and may require medical or surgical intervention to prevent one of the outcomes listed in the above definition .

Additional Guidance For Hospitalizations

Hospitalization is not a SAE; it is an action due to an adverse event (AE), serious adverse event (SAE) or unanticipated problem or experience. Hospitalization for an elective procedure or surgery for a pre-existing condition that has not worsened is not a serious adverse event; however, is must be reported as an adverse event (AE).

It requires reporting of all hospitalizations including elective admissions and all deaths even if unrelated to investigational treatment.

Unanticipated Adverse Effects

An unanticipated adverse effect is any serious adverse effect on health or safety or any life-threatening problem or death caused by, or associated with, a device, if that effect, problem, or death was not previously identified in nature, severity, or degree of incidence in the investigational plan or application (including a supplementary plan or application), or any other unanticipated serious problem associated with a device that relates to the rights, safety, or welfare of subjects.)

SAE Reporting in Long-Term Follow-Up Studies

Reporting of hospitalizations is not necessary for subjects enrolled in long-term follow-up studies in which the subjects are receiving no investigational treatment. Other hospitalizations that are part of the disease process do not have to be reported unless they have increased in severity or frequency or if requires notification.

Deaths

All deaths within 30 days post-surgery must be reported, regardless of relationship to study intervention or disease progression to the respective ethics committee. The research team should report any death, regardless of the time point, as soon as they become aware of the event to the main study site

Serious Adverse Events Review

The DSMB reviews all serious adverse events.

Requirement of Reporting Form

All local subjects (e.g., those followed by our investigators) unexpected adverse events, unanticipated problems, or serious adverse events must be reported to EXPEL Study Team.

The File number, the protocol title, the Principal Investigator's name and the name of the person submitting the report must be included. The report must also provide the subject identification number, a statement that the PI has reviewed the information and the PI's signature. A copy of the adverse event or serious adverse event form(s) may be provided as supplemental information.

8.2. Safety Monitoring Plan

The purpose of the Data and Safety Monitoring Plan is to ensure the safety and well-being of study subjects, and the integrity of the data collected for the study. A Data Safety Monitoring Board (DSMB) would be appropriate way to monitor data as this is a large study population with multiple study sites. This includes a combination of the Principal Investigator and experts within the institution, [name] (National Cancer Centre, Tokyo, JCOG Operations) A/[name] (NUS SPH), [name] [name] (NUS Medicine Dean's Office)

The review of the adverse events/ serious adverse events data will be monitored to study the safety and compliance of the trial. UPIRTSO Reporting will be done according to the DSRB guidelines.

The stopping criteria for the research study will based on futility that the study question will not be answered when the study is completed.

The route of dissemination of any data and safety information can be communicated to the study sites via regular emails and at ad-hoc meetings, the person/team responsible for doing so will be initiated from the Principal PI and the sites PI.

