9. DATA ANALYSIS

9.1. Data Quality Assurance

The PI, study coordinator and the biostatistician in the study team will ensure the quality of the data. Annual interim analysis will be conducted out every year from external party. Onsite monitoring services engaged from commercial company will be done for sites with high volume subjects. Web randomization system will undergo audit as well.

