9.2. Data Entry and Storage

The study team would store all research data within the institution. The research data (hardcopy) will be stored and the location storage is secured (data stored in research team office location with lock and key access. Storage of records are locked in file cabinets) There is limited access to the study data. Only the PI and study coordinator will have access to the research data. According to SGGCP and the NHG research policy recommends, the essential documents should be retained a minimum storage until 6 years after the completion of the clinical trial.

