10.2. Statistical and Analytical Plans

The data will be analysed as intention-to –treatment basis. Survivals are calculated using Kaplan-Meier method. Peritoneal recurrence is based on clinical and radiological findings. A p-value <0.05 is considered as statistically significant.

An interim analysis was performed on 350 subjects with 6 month follow up data. Data Safety Monitoring Committee recommended that at least another 200 subjects to be recruited. Hence the original target recruitment of 600 subjects is being changed to 800 subjects in this protocol.

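### The Principal Investigator is listed as a member of the DSMB, and nothing in the protocol keeps interim results by arm from that person or from the board's size and stopping recommendations

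*Protocol*

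**What the plan says.** Section 8.2 proposes a DSMB because the trial is large and multi-site, and its next sentence describes the composition: "This includes a combination of the Principal Investigator and experts within the institution". Members from other bodies follow in the same list. The section adds a futility-based stopping criterion without a threshold, and has the lead PI and the site PIs start the dissemination of data and safety information.

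Other sections give the board its reach:

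- Section 3.5 allows the study to be closed after DSMB review.
- Section 8.1 has the DSMB review every serious adverse event.
- Section 10.2 reports: "An interim analysis was performed on 350 subjects with 6 month follow up data". It continues: "Data Safety Monitoring Committee recommended that at least another 200 subjects to be recruited". The consequence is drawn directly: "Hence the original target recruitment of 600 subjects is being changed to 800 subjects in this protocol".

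On who handles data, section 9.1 says "Annual interim analysis will be conducted out every year from external party" and "The PI, study coordinator and the biostatistician in the study team will ensure the quality of the data". Section 9.2, repeated in section 13, says "Only the PI and study coordinator will have access to the research data".

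On blinding, section 6 says only: "The randomisation code will be disclosed to the surgeon only at the end of gastrectomy".

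**The concern.** A monitoring board is useful because the people running the trial do not know how the arms compare while they can still influence it. Here the person leading the trial is placed on the board. The protocol provides no closed session, no recusal and no rule withholding results by arm.

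The allocation is known to the surgeon, and no blinding of patients or outcome assessors is described. A PI who knew the interim comparison could affect the vigour of recruitment, the care given after surgery, the reading of possible recurrence, and the timing of later looks. Peritoneal recurrence is judged on clinical and imaging grounds, so it is open to such influence.

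The size change raises a separate problem. It followed an interim analysis and came on the advice of the monitoring committee. With the PI on that committee, the sponsor cannot show from this protocol that the increase was advised without the trial's leader knowing the results.

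**Working it through.** The point concerns governance, so the main check is to set the sections side by side. Two calculations then size the consequence.

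**Reading the sections together**

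1. *Is the PI on the board?* In 8.2 the composition sentence comes straight after the DSMB is introduced, and the DSMB is its natural subject. The protocol does not say whether the PI votes.
2. *Is it the same body that advised the increase?* Section 10.2 calls it a committee and 8.2 calls it a board. The protocol describes only one such body, so I take them to be the same.
3. *Does anything separate the PI from results by arm?* The one element of independence is the external party that performs the annual interim analyses (9.1). Nothing says to whom it reports or that the PI is kept from its reports.
4. *Does the data-access sentence settle it?* No. It sits in a paragraph on locked storage. Taken literally it would shut out the study biostatistician and the external party, both of whom need data under 9.1. It needs rewording, and as written it places no limit on the PI.

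**Is the size change explicable without results by arm?**

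Inputs from 10.1: survival 60% and 70%, HR 0.7, 80% power, two-sided 5%, equal allocation. Stated result: 800.

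- Two proportions: n per arm = [1.96√(2×0.65×0.35) + 0.842√(0.6×0.4 + 0.7×0.3)]² / 0.1² ≈ 356, total 712 (752 with continuity correction).
- Schoenfeld: events = 4(1.96 + 0.842)² / (ln 0.7)² ≈ 247. At a mean event rate of (0.40 + 0.30)/2 = 0.35, N ≈ 706. Freedman gives 253 events, N ≈ 723.
- The stated inputs alone do not return 800. An unstated 10% dropout allowance comes close: 712/0.9 ≈ 792, and about 804 from Freedman.
- Power at 600: 0.35 × 600 = 210 events; √210/2 × |ln 0.7| − 1.96 ≈ 0.62, so about 73%. At 800 (280 events) it is about 85% (84% by two proportions).

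On the plan's own assumptions the target of 600 was therefore short of 80% power, and an increase could be justified without any comparison of the arms.

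**Worst-case effect on the final test**

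Suppose the choice between 600 and 800 had been made from results by arm in the most damaging way, with the final test left at 0.05. Let I₁ be the information at the look, I the final information, c = 1.96 and z₁ the interim statistic. The conditional error is 1 − Φ[(c√I − z₁√I₁)/√(I − I₁)]. Take the larger of its values at I = 600 and I = 800, integrate over the null distribution of z₁, and double.

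The protocol gives no death count at the look, so the information fraction is an assumption. The top of the range is 350/600 = 0.583. It is likely too high, because only six months of follow-up were used.

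| Assumed fraction of the 600-patient information | Two-sided type I error, at most |
|---|---|
| 0.05 | 0.051 |
| 0.10 | 0.052 |
| 0.20 | 0.053 |
| 0.30 | 0.054 |
| 0.40 | 0.055 |
| 0.583 | 0.057 |

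This covers that single choice only, not the other annual looks.

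**The case against.** The strongest reply is that the protocol shows no breach. Several stronger readings are tempting, and the documents do not support them.

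- *The PI has seen comparative results.* Nothing says so. Section 10.2 does not state that the interim analysis was by arm or who received it, and 9.1 gives the analyses to an external party. What stands is that the PI can see them and nothing prevents it.
- *Only two people hold the data.* That is the wording of a storage clause, and 9.1 shows it cannot be literal.
- *Sections 8.2 and 9.1 contradict each other on independence.* They do not. An external analyst can report to a board that includes the PI.
- *Eligibility decisions could differ by arm.* Staging is judged during the operation and the code is disclosed only at the end of gastrectomy, so this route is weak.
- *The PI recruits the patients.* This is not stated. Study-team clinicians make first contact and a research nurse takes consent in the doctors' absence. The largest site target visible in Table 1 is 150 of 800, or about 19%.
- *The increase was driven by results.* The committee advised it, the PI is one voice among several, and about 73% power at 600 is a sufficient innocent reason.

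Overall survival is also an objective endpoint. A charter not shown may contain session rules.

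These replies narrow the point but do not remove it. Membership is stated in the protocol and is not a detail left to another document. A charter that excluded the PI would conflict with 8.2.

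**Conclusion.** The point holds as a defect in a stated membership rule. The PI belongs to a board that reviews all serious adverse events, can close the study on an unquantified futility criterion, and whose advice after an interim look raised the target by 200/600, or one third. No provision keeps results by arm from the PI.

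The exposure lies in trial conduct, in disease-free survival and peritoneal recurrence, and in how defensible the move from 600 to 800 is. Assessment of overall survival is not in question. The worst-case inflation from the size choice is modest, about 0.051 to 0.057 against 0.05, so the harm is mainly to credibility.

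This rests on three assumptions: that the composition sentence in 8.2 describes the DSMB, that the committee in 10.2 is the same body, and that the information fraction lay between 5% and 58%. Since annual looks are planned, a correction can still protect later decisions.

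**What to change.** - Amend 8.2 so that the PI and study-team members are not voting members of the DSMB and attend open sessions only. Reports by arm go from the external party in 9.1 to the remaining members alone.
- Reword the data-access sentence in 9.2 and section 13 to agree with the roles in 9.1, and to bar the PI and study coordinator from outcome summaries by arm before the final analysis.
- Record what the PI saw, and when, at the 350-subject look. If it included nothing by arm, that statement is the best defence of the increase to 800.

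The cost is a short amendment and, if a charter exists, a matching change to it. The external party and members from other bodies are already provided for. Names are removed from the text, so the sponsor should confirm that enough of the remaining members are outside the study team. The small downside is that the PI loses sight of interim data by arm.
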